To date, there is no study reporting the rate of response in participants using MAD. Due to lack of preliminary data and effect size, estimates of the sample size for this study will be determined based on feasibility. We propose a pilot study with a total sample size of 60 subjects (snorers only). The sample size of 60 subjects is feasible, given the incidence of primary snoring prevalence in America, which is estimated at 40-50%¹⁵. Using a 33% drop out rate, we estimate that the sample size of 60 subjects randomized in a balanced way between the two treatment groups will provide us with 40 evaluable cases. We hypothesize that the rate of the responders in the MAD group will be 20% higher than the rate of responders in the active control group. If the rate of response in the control group is 30%, the sample size of 20 subjects per group will allow us to estimate a 95% confidence interval around the rate difference between groups with a margin of error of 30%.

F2 Interim Monitoring and Early Stopping

Due to the size of the study and the nature of a pilot study, we will not be participating in early stopping or interim monitoring of the participants.

F3 Analysis Plan

A Per Protocol analysis will be used for the primary analysis of the data. Descriptive statistics will be used to describe the characteristics of participants in the 2 study groups. Responder rate difference will be calculated as shown below:

Responder Rate:

$$\text{Responder}_{\text{Conservative}} / \text{Total Participants}_{\text{Conservative}}$$
$$\text{Responder}_{\text{MAD}} / \text{Total Participants}_{\text{MAD}}$$

Responder Rate Difference:

$$\Delta_{\text{Responder Rate}} = \text{Responder}_{\text{Conservative}} - \text{Responder}_{\text{MAD}}$$

95% confidence interval around the difference will be calculated and reported. Chi square test or Fisher's exact test will be used to compare categorical level outcomes between the 2 study groups, including the difference in Responder Rate. Effect sizes and 95% CIs will be reported for each comparison. For secondary outcomes, independent samples t-test or its non-parametric equivalent Mann-Whitney U test will be used to compare continuous level outcomes between the 2 study groups. Median or mean difference and CI will be calculated and reported according to the test being used. The role of potential confounders will be explored in multivariate analysis using logistic regression or GLM. All statistical analyses will be conducted in SPSS 28 (IBM Corp., Armonk, NY).

F4 Missing Outcome Data

All attempts will be made to minimize the occurrence of missing outcome data through adherence to the principles of Good Clinical Practice and the reduction of the complexity and number of assessments. It is assumed that all missing data will be at random. As this is a small pilot study, no computational techniques will be employed to adjust analyses for missing data.

F5 Unblinding Procedures

After all data analysis and charts, tables, and graphs are created, unblinding will occur. [name] will break the blind and all placeholders in the manuscript and graphics will be replaced with the corresponding intervention.

G Data Handling and Record Keeping

G1 Confidentiality and Security

Procedures are in place to curb risks of breaches in confidentiality and privacy. These procedures include: 1) formal training protocols centered on the maintenance of confidentiality for all study team members; 2) a password-protected computer file that contains the identity of participants, corresponding ID numbers, and contact information; 4) secure storage for identified data forms such as completed questionnaires; and 5) communication with study team via secure email, phone line, or tele-video call.

Only members of the study team will have access to the electronic research files. All research data files will be stored on secure Washington University servers with computer, network, and database-level passwords that will only be accessible to study team members. No participant identifying information will be revealed in any publications or presentations.

Case report forms will be created as electronic documents and stored within each study participant's electronic file. Original hard-copy source documents will be electronically scanned and stored in the participant's electronic file and stored in a locked file cabinet.

G2 Records Retention

All records will be retained for a minimum of six years after completion of the study and closure with the WU IRB. Data will be stored for contribution to future research studies. Contribution for future use is optional for participation in the study

H Study Administration

H1 Participant Payment

Participants will be provided a Forte/Advarra debit card. They will receive \$30 for completing each set of surveys associated with the study. As such, a participant may receive \$60 total. This will be payable to the participant upon completion of the study. If participants do not complete all requirements, they will be paid proportionally for the work they have completed. Participants will be able to keep all items received as part of their respective treatment arm. The sleeping partner will be paid an additional \$25 for responding to > 80% of the texts. If they respond to > 50% of the texts they will receive \$10. If the sleeping partner's response rate is <50% they will not be compensated for the texts.

H2 Study Timetable

Participants will be in the study for a total of eight weeks. Given the volume of patients seen at the Adult Division of the Department of Otolaryngology-Head & Neck Surgery and the Sleep Medicine Center for assessment of snoring, we anticipate it will take one year to complete enrollment, intervention, and analysis.

	Months											
	1	2	3	4	5	6	7	8	9	10	11	12
Enrollment and Baseline Assessment												
Randomization												
Pre-intervention period									1			
4 week intervention treatment												
End of participation assessment												
Data analysis and Manuscript preparation												

*Pre-intervention period is the 4-week period prior to the intervention where the MAD will be adjusted or the Mometasone nasal rinse is ongoing.

I Publication Plan

We plan to analyze accumulated data throughout the month of May 2023 and publish the results by the end of June 2023. This data includes the analysis of the CGI-I, CGI-S, SNORE-25, and ESS as well as a discussion of the potential adverse effects associated with Mandibular Advancement device and standard therapy for treatment of non-apneic snoring.

J Attachments

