F1	SAMPLE SIZE DETERMINATION AND POWER	19
F2	INTERIM MONITORING AND EARLY STOPPING.....	19
F3	ANALYSIS PLAN	19
F4	MISSING OUTCOME DATA.....	20
F5	UNBLINDING PROCEDURES	20
G	DATA HANDLING AND RECORD KEEPING	20
G1	CONFIDENTIALITY AND SECURITY	20
G2	RECORDS RETENTION	20
H	STUDY ADMINISTRATION	20
H1	PARTICIPANT PAYMENT	21
H2	STUDY TIMETABLE	21
I	PUBLICATION PLAN	21
J	ATTACHMENTS	22
J1	INFORMED CONSENT DOCUMENTS	22
J2	PATIENT EDUCATION BROCHURES	22
J3	QUESTIONNAIRES OR SURVEYS.....	22
K	REFERENCES	22

A Introduction

A1 Study Abstract

Introduction: Snoring is a problem affecting nearly 40% of the adult population and which leads to adverse health outcomes in the participant and sleeping partner. Despite the large number of people affected, insufficient research exists in the published medical literature documenting treatment effectiveness for primary snoring. Contrary to this, a large amount of research exists on effective treatment for sleep apnea; from this comes our understanding of the treatment effectiveness for snoring. The goal of this study is to determine whether Mandibular Advancement Devices (MAD) are an effective treatment for primary snoring when compared to conservative therapies.

Methods: This study will consist of a randomized control trial of adult participants with non-apneic snoring. Participants will be recruited from an academic medical center and randomized into either conservative therapy that is medicated nasal rinses, external nasal dilator, mouth taping, and lateral positional therapy or Mandibular Advancement Device. Participants and their sleeping partner will be evaluated at baseline and at follow up with a modified Clinical Global Impression (CGI) Scale. At baseline, they will be evaluated with a CGI-Severity scale, and at follow up with a CGI-Improvement scale. The primary outcome is the Snoring Clinical Global Impression Scale-Improvement for the sleeping partner. Secondary outcomes include change in the Epworth Sleepiness Scale (ESS) in the participant, change in ESS in the sleeping partner, CGI-I Scale for the participant, change in the SNORE25 for the participant, and change in SNORE25 for the sleeping partner.

A2 Primary Hypothesis

We hypothesize that the Mandibular Advancement Device (MAD) will result in a clinically meaningful, statistically significant difference in the modified Snoring CGI-I Scale when compared to the conservative therapy for participants with non-apneic snoring as measured by their sleeping partner.

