The secondary aim is to evaluate the effectiveness of treatment of snoring on the sleeping partner's sleep quality as measured by the *CGI-I* scale, the *Epworth Sleepiness Scale (ESS)*, and a modified *Symptoms of Nocturnal Obstruction and Related Events (SNORE-25)* questionnaire.

C3 Rationale for the Selection of Outcome Measures

Primary Outcome:

Clinical Global Impression of Improvement Scale (CGI-I) - Partner: To address the primary aim, the primary outcome measurement is the CGI-I Scale in the sleeping partner. The CGI-I will pose the question “Overall, how do you rate the response to snoring treatment?”, with 7 response options including: *Very Much Improved, Much Improved, Minimally Improved, No Change, Minimally Worse, Much Worse, and Very Much Worse*. The CGI-I is adapted from a previously validated measure commonly used in psychiatric studies, and is a self-report scale²¹. Participants will be measured after completing 4 weeks of their respective intervention. As snoring primarily effects the sleeping partner, the sleeping partner's responses will be the primary outcome measurement. A sleeping partner who rates the response to treatment as either *Very Much Improved* or *Much Improved* will be graded as a responder to treatment. The percentage of responders to non-responders will be compared between the two treatment arms.

Secondary Outcomes:

1. **CGI-Improvement Scale - Participant:** The CGI-I will be administered to the participant in the same method as described above.
2. **CGI-Severity (CGI-S) Scale - Partner and Participant:** The CGI-Severity Scale poses the question “On average, how much of a problem does your [partner’s] snoring pose?” The 5 response options will include: no problem, mild problem, moderate problem, severe problem, problem as severe as it can be. It will be measured both at baseline and after treatment. In addition, the CGI-S will be measured by the sleeping partner on a daily basis both before and after treatment.

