This study is a randomized control trial with an active control group. Once participants are enrolled in the study, all baseline measures and demographic information will be recorded by the participant and their sleeping partner (*Demographics*, *DemographicsPartner*, *BaselineData*, and *BaselineDataSleepingPartner*). After the baseline measures are recorded, participants will be randomized to receive either MAD or the standard conservative therapy. The MAD arm will consist of participants given a fitted mandibular advancement device that they will wear for the length of the study. The device will be fully fitted by the maxillofacial physician who specializes in maxillofacial prosthodontics, and is an expert at the fabrication of mandibular advancement devices. The standard home therapy will include daily use of medicated nasal rinses, external nasal dilator, mouth taping, and lateral positional therapy and will function as our active control group.

For those randomized to the MAD, we will arrange a meeting with the maxillofacial physician to initiate the process of fitting the device. After the device is fully fitted, which will take 4 weeks, the participants will initiate the 4-week intervention.

For those who are randomized to the standard conservative therapy, it will begin with a medicated nasal rinse (Neti-cort – nasal saline lavage with Mometasone), which will take 4 weeks to achieve therapeutic effectiveness for improved nasal breathing. After the 4 weeks of Neti-cort therapy, the standard therapy group will begin their intervention for 4 additional weeks as well. Participants in the standard home therapy will have access to an instructional video library which will correctly demonstrate how to implement the home therapies.

The sleeping partners will receive a text message each morning from the day of enrollment until study completion. The content of the text message will be the CGI-S and the sleeping partner will respond to the text message each morning.

Participants will use the intervention nightly for a period of 4 weeks after which an end of study visit will occur. At the end of study visit, all post-intervention outcomes will be recorded.

D2 Subject Selection and Withdrawal

2.a Inclusion Criteria

Participants will be recruited based on the following inclusion criteria:

- Age ≥ 18
- Report of snoring

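### The primary CGI-I question names no comparison point and the two lead-ins differ, so partners in the two arms may rate against different reference periods

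*Combined protocol and SAP*

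**What the plan says.** C3 makes the partner's CGI-I the primary outcome and gives the wording of the item: "Overall, how do you rate the response to snoring treatment", with seven options. A partner who chooses one of the top two (Very Much Improved or Much Improved) "will be graded as a responder to treatment". On timing, C3 says "Participants will be measured after completing 4 weeks of their respective intervention". Neither the question nor the text around it names a baseline, a visit or a recall period. The nearest thing to a reference is in A1: "At baseline, they will be evaluated with a CGI-Severity scale, and at follow up with a CGI-Improvement scale".

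The arms spend the first 4 weeks differently. In D1, control therapy starts with a mometasone rinse, "which will take 4 weeks to achieve therapeutic effectiveness for improved nasal breathing". For the device arm, D1 says "After the device is fully fitted, which will take 4 weeks, the participants will initiate the 4-week intervention".

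The protocol then gives two accounts of the rinse weeks. D1 has conservative therapy starting with the rinse, and 3a.2 counts the rinse among the four conservative interventions. But D1 also says "After the 4 weeks of Neti-cort therapy, the standard therapy group will begin their intervention for 4 additional weeks as well", and the H2 footnote says "Pre-intervention period is the 4-week period prior to the intervention where the MAD will be adjusted or the Mometasone nasal rinse is ongoing".

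**The concern.** Identical wording in both arms does not guarantee an identical reference. Two starting points are open to a partner: snoring at enrolment, or snoring when the 4-week intervention began. For a MAD partner both are largely untreated states. For a control partner the first is untreated and the second follows 4 weeks of nightly rinse.

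If the rinse reduces snoring and a control partner rates from the later point, that benefit drops out of the rating. The responder rule dichotomises the scale between Much and Minimally Improved, so a one-category shift at that cut turns a responder into a non-responder. The difference arises after randomisation, so randomisation does not balance it. Coding the groups as A and B for analysis (2.e, 3.h) and the confounder models in F3 do not address it either.

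**Working it through.** **Inputs.** From F1: 20 evaluable per group, control responder rate 30%, MAD rate 20 points higher (50%), 33% dropout from 60 randomised, 95% interval with a 30% margin of error. From C3: responder = top two of seven categories. From E4: first fitting visit within 2 weeks, manufacture 7 to 10 days, second meeting inside the 4-week lead-in.

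**The plan's own figures.**
- Evaluable: 60 × (1 − 0.33) = 40.2, so about 20 per arm.
- Margin of error: 1.96 × √(0.30 × 0.70/20 + 0.50 × 0.50/20) = 1.96 × √0.0230 = 0.297, against the stated 30%. Both figures reproduce. This margin covers sampling error only, not a shift in what is being rated.

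**How different the lead-ins are.** On E4's timings a MAD participant could be without a device for up to 14 + 10 = 24 of the 28 days. E4 also has self-titration taught at the second meeting, within the lead-in, so some device use before week 4 is possible. Sections 3a.1 and 3.d, which describe a single fitting visit and delivery of the device at the initial visit, do not agree with D1 and E4. The MAD lead-in is therefore closer to untreated than the control lead-in, but cannot be called fully untreated.

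**Effect of one reclassified control partner.** 1/20 = 5 percentage points, and only if that partner crosses from Much to Minimally Improved. A move from Very Much to Much leaves the partner a responder. A move that starts below the cut changes nothing.

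**Effect of a misclassified share.** Let p be the true control responder rate and m the share of true control responders scored as non-responders. The observed control rate is p(1 − m), and the difference (MAD minus control) shifts by p × m. The documents give no value for m; those below are assumptions.

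| m (assumed) | Observed control rate (p = 30%) | Observed difference (true 20) | Shift at p = 30% | Shift at p = 50% |
|---|---|---|---|---|
| 10% | 27% | 23 points | 3 points | 5 points |
| 20% | 24% | 26 points | 6 points | 10 points |
| 30% | 21% | 29 points | 9 points | 15 points |

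The shift is the same if the arms do not truly differ: at 30% in both, these shares would produce an apparent MAD advantage of 3 to 9 points.

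**How far this could go.** At a 30% rate, 0.30 × 20 = 6 control responders are expected. Losing 2 of them (10 points) means m = 2/6 = 33%. Losing 4 (20 points, the whole hypothesised effect) means m = 4/6 = 67%.

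**The case against.** The strongest reply is that a partner asked for an overall rating of the response to snoring treatment will naturally judge the whole treatment, rinse included, against untreated snoring. The pre-intervention label sits in protocol text, and nothing shows that partners see it. Section 3.h has both interventions explained to participants before randomisation, and A1 pairs severity at baseline with improvement at follow-up. Many partners may well rate as intended. But that reference is only implied, and the protocol itself places the start of control treatment at two different times.

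A reader might infer more: that the wording biases the trial toward MAD, perhaps by as much as the full 20 points. The documents do not support that. The direction holds only if some control partners anchor at week 4 and the rinse helps. If control partners rate from enrolment, they judge about 8 weeks of some active treatment against about 4 for MAD, which could favour control. The full 20 points would need two-thirds of the expected control responders to be misclassified.

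Two further points stand in part. The partner's follow-up form listed in J3 is not reproduced and might carry an anchor, but the protocol gives the question without one. Partner CGI-S is collected at baseline, daily from enrolment and at the end, so improvement during the rinse weeks can be seen. It is a secondary outcome on another scale and cannot repair the primary item.

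**Conclusion.** The point holds as a possible, unquantified bias. Three things come from the text: the primary item has no stated comparison point, the lead-ins differ, and the protocol conflicts on whether the rinse weeks are treatment. Together they let the reference point differ by arm. The bias favours MAD if some control partners anchor at the end of the rinse weeks and the rinse works; otherwise its direction is open.

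The shift of 3 to 9 points is an illustration that rests on the F1 control rate of 30% and an assumed misclassified share of 10 to 30%. It is smaller than the 30-point margin of error, but it is systematic, and the interval does not allow for it. Once ratings are collected, the reference each partner used cannot be recovered.

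**What to change.** 1. Anchor the CGI-I stem to before enrolment, identically in both arms and worded for each rater, keeping the seven options and the responder rule. For the partner: *Compared with before you joined the study (Visit 1), overall, how has your partner's snoring responded to the study treatment?* For the participant, the same with *your snoring*. Put the wording in C3 and in the follow-up forms. If those forms already carry an anchor, quote it in C3.
2. Reconcile D1, 3a.2 and H2 on whether the rinse weeks count as treatment.
3. Pre-specify change in partner CGI-S from the pre-randomisation baseline as a supportive analysis.

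The cost is re-approval of one sentence in the survey. If any end-of-study ratings have already been collected, the two wordings will be mixed, and the date of the switch must be documented. Sample size, visits and treatment do not change. The anchor gives both arms the same reference; it does not remove the unequal length of exposure, about 8 weeks of some treatment in control against about 4 with the device.

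### F3 has no analysis suited to the daily partner CGI-S: specify one 28-night mean per partner, adjusted for the Visit 1 rating

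*Combined protocol and SAP*

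**What the plan says.** C3, secondary outcome 2, has the CGI-S rated by participant and partner at the two visits: "It will be measured both at baseline and after treatment". It then adds a second stream from the partner alone: "the CGI-S will be measured by the sleeping partner on a daily basis both before and after treatment". D1 sets the schedule: "The sleeping partners will receive a text message each morning from the day of enrollment until study completion". E5 repeats it, and H2 gives the length: "Participants will be in the study for a total of eight weeks".

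F3 names three kinds of analysis.
- Categorical outcomes: chi-square, or "Fisher's exact test will be used to compare categorical level outcomes between the 2 study groups".
- Continuous secondary outcomes: "independent samples t-test or its non-parametric equivalent Mann-Whitney U test will be used to compare continuous level outcomes".
- Logistic regression or GLM, to explore confounders.

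F3 does not mention the daily series. It defines no per-partner summary, no time window and no model with partner as the cluster. F4 assumes missing data are at random and adds that "no computational techniques will be employed to adjust analyses for missing data". Section I commits to analysing the CGI-S but does not say whether that means the visit ratings, the daily ratings or both.

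**The concern.** Ratings given by the same partner on successive mornings are correlated, and the group comparisons in F3 are valid only with one independent value per partner. Some step must therefore reduce each series to one value, or model the clustering, and the plan does not supply it.

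Two things are at stake. First, an analyst could choose the window (all 56 mornings, the last 28, or a change between periods) and the unit of analysis after seeing the data. Second, F3's unadjusted tests leave out a CGI-S that E3 records before randomization and that could be used as a covariate at no cost.

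The window matters because of what happens before the intervention starts. D1 and D3 (3b.2) have the conservative arm using the mometasone rinse for four weeks, while the MAD arm is having its device made and fitted. Those mornings come after randomization and are not an untreated baseline in both arms, so a before-to-after change in the daily ratings would not mean the same thing in each arm.

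**Working it through.** **The plan's own figure.** F1 gives a 30-point margin for the responder-rate difference with 20 evaluable per arm, 30% in controls and 20 points more with MAD (reading 20% as absolute): 1.96 × √(0.3×0.7/20 + 0.5×0.5/20) = 1.96 × √0.023 = 0.297. It reproduces. It concerns the partner CGI-I, one value per partner, so the present point does not touch it.

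**Inputs.**
- Evaluable partners: 20 per arm (F1).
- Mornings: 8 × 7 = 56, of which 28 fall in the four-week intervention period (D1, H2). These are maxima. H1's payment tiers foresee missed texts: more than 80% of 56 means at least 45 answers, and more than 50% means at least 29.
- Within-partner correlation r: not in the documents. It is assumed and varied.

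**What pooling would do.** With m ratings per partner the design effect is DE = 1 + (m − 1)r. A pooled standard error is too small by a factor of √DE, and a nominal two-sided 5% test rejects a true null with probability 2 × [1 − Φ(1.96/√DE)].

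| r | DE, m = 28 | √DE | False positives, m = 28 | DE, m = 56 | False positives, m = 56 |
|---|---|---|---|---|---|
| 0.05 | 2.35 | 1.53 | 20% | 3.75 | 31% |
| 0.1 | 3.7 | 1.92 | 31% | 6.5 | 44% |
| 0.3 | 9.1 | 3.02 | 52% | 17.5 | 64% |
| 0.5 | 14.5 | 3.81 | 61% | 28.5 | 71% |
| 0.7 | 19.9 | 4.46 | 66% | 39.5 | 76% |

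**Check by simulation.** 2,000 trials per setting with no treatment effect, 20 partners per arm, a five-level scale, 28 nights and r = 0.3, 0.5, 0.7.
- All texts answered: the pooled t-test rejects in 51.7%, 60.6% and 64.8% of trials; the t-test on partner means in 5.0%, 4.9% and 5.7%.
- 80% of texts answered: the pooled t-test rejects in 45%, 56% and 63%.
- 80% answered, over r = 0.1 to 0.7 and both 28 and 56 nights: partner means reject in 4.1% to 5.6% by t-test and 4.2% to 5.2% by Mann-Whitney.

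So F3's own tests are sound once each partner contributes one value.

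**Whether GLM fills the gap.** F3 does not define the term and gives it only for confounders. If it meant a repeated-measures GLM needing complete series, few partners would remain. With independent misses, the share answering all 28 mornings is 0.95^28 = 24%, 0.90^28 = 5% and 0.80^28 = 0.2%.

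**The case against.** The strongest reply is that nothing in the plan proposes a wrong analysis. A reader might infer from F3 that the daily ratings must be either pooled as independent or discarded. The documents do not support that. No section says either, F3's responder rates are counted per participant, and a per-partner mean fits the t-test or Mann-Whitney test without changing them. The false-positive rates above therefore describe a misuse that the plan leaves open, not a property of the plan, and they depend on assumed correlations. That part of the reply stands.

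A reader might also infer that relying on the Visit 2 CGI-S would lose most of the information. The documents do not show this. That item asks for an average judgement, not a rating of one night, and no variance is given for it, so the gain from the daily mean over the visit rating cannot be put in figures.

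It can also be said that the stakes are modest. This is a feasibility-sized pilot, CGI-S is missing from the secondary outcomes in A1 and from the aim in C2, and the visit ratings can be analysed under F3. That is fair and limits the weight of the point. But C3 and E8 list CGI-S as an outcome, Section I promises its analysis, and partners are asked for a rating every morning and paid by response rate. The summary that would make F3 work is the piece that is not written down.

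**Conclusion.** The point holds as a gap with an easy improvement. The daily partner CGI-S is a planned secondary outcome of up to 56 correlated ratings per partner. F3 has no analysis suited to it, and its unadjusted two-sample tests do not use the pre-randomization rating.

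The size is conditional. If 28 nights were pooled as independent, the false-positive rate would be about 52% to 66% for r = 0.3 to 0.7, and still 20% at r = 0.05. One mean per partner keeps it near 5%. These figures assume an equal correlation between all nights of a partner and 20 evaluable partners per arm. The primary outcome, its 30-point margin and the visit CGI-S are unaffected. The change should be made, but the trial's main conclusion does not depend on it.

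**What to change.** Add one paragraph to F3:
- The daily outcome is each partner's mean CGI-S over the 28 intervention nights, from the answered mornings. State the numerical scoring of the five categories.
- Arms are compared by a linear model with the partner's Visit 1 CGI-S as covariate, reporting the adjusted difference with a 95% confidence interval.
- The four pre-intervention weeks are not used as baseline, because controls already use the mometasone rinse then while the MAD is being fitted. Those ratings may be shown descriptively.
- Nights are never treated as independent observations.

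As an alternative or sensitivity analysis, fit a linear mixed model with a random partner intercept to all answered intervention mornings. It is close to the analysis of means but not identical when texts are missed, because it weights partners differently by how many mornings they answered. Amend F4 to allow this model and to say how unanswered texts are handled, since its present wording could be read as excluding it.

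The cost is a paragraph in F3, a sentence in F4 and a short step in the SPSS version already named. No new data are needed.
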